**3.3.1. Risk Assessment**

Potential Risk of Clinical Significance	Summary of Data/Rationale for Risk	Mitigation Strategy
Investigational Product (IP) GSK3036656		
Reduction in red blood cell count	
Non-Clinical
 
In a 4-week rat study (doses 3, 10 & 30 mg/kg/d) - dose-dependent decline in reticulocytes (by up to 52% in males and 62% in females) at day 7 followed by normal levels by day 14 and increased levels by day 29/30 compared to controls. Hgb levels decreased by 10-13% compared to controls on day 14 and day 29/30.
 
In a 4 week dog study (doses 5, 10 & 20 mg/kg/d) - mild dose-dependent decrease in Hgb on day 14 (by about 10% compared to controls) with recovery by week 4. Reticulocyte counts unaffected. Dogs not bled on day 7.
 
No histopathological changes in bone marrow or other relevant histopathology in the 4-week studies.
 
Clinical
 
In the 201040 study, a possible trend of decreased haemoglobin from baseline to follow-up was noted in aggregate haematology data. The mean change
	
Standard safety haematology and clinical chemistry assessments will be performed and both trends and changes outside normal range will be monitored as part of laboratory safety assessments.
 
Participants whose haemoglobin drops below pre-specified limits will be withdrawn from the study (Section 8.1.3).

Potential Risk of Clinical Significance	Summary of Data/Rationale for Risk	Mitigation Strategy
	
from baseline to follow-up was -4.9 g/L in the 15 mg repeat dose cohort, compared to -1.5 g/L in the placebo group. None of the values hit potential clinical importance (PCI) criteria, and declines were not clinically relevant.
 
No clinically significant trends in reticulocyte values were observed, and there were no values of potential clinical importance reported for reticulocytes.
	
GSK3036656 is cleared through the kidneys	The main route of clearance for GSK3036656 is renal and there is therefore a risk that participants with low creatinine clearance will accumulate GSK3036656 and exceed predefined exposure limits.	Participants with a creatinine clearance less than 75 mL/min have been excluded.

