## 6.2. Exclusion Criteria

Participants are excluded from the study if any of the following criteria apply:

1. Evidence of a clinically significant (as judged by the Investigator) condition or abnormality (other than the indication being studied) that might compromise safety or the interpretation of trial efficacy or safety endpoints.
2. Poor general condition where any delay in treatment cannot be tolerated per discretion of the Investigator.
3. Clinically significant evidence of extrathoracic TB (miliary TB, abdominal TB, urogenital TB, osteoarthritic TB, TB meningitis), as judged by the Investigator.
4. QTcF > 450 msec.
5. History of allergy to any of the trial IP/s or related substances as confirmed by the clinical judgement of the Investigator.
6. Participants with vitiligo.
7. Current alcohol or drug abuse, that is, in the opinion of the Investigator, sufficient to compromise the safety or cooperation of the participant.
8. HIV infected participants:
  - a. having a CD4+ count <350 cells/ $\mu$ L;
  - b. or having received antiretroviral therapy medication within the last 30 days;
  - c. or having received oral or intravenous antifungal medication within the last 30 days;
  - d. or with an AIDS-defining opportunistic infection or malignancies [CDC, 1993] in the last 12 months (except pulmonary TB).
9. Participated in other clinical studies with investigational agents within 8 weeks prior to the first dosing day in the current study.
10. Participants with diabetes (Type 1 or 2), point of care HbA1c above 6.5 %, or random glucose over 11.1 mmol/L will be excluded from cohorts undergoing CCI

11. Treatment received with any drug active against Mtb (including but not limited to isoniazid, ethambutol, fluoroquinolones, rifampicin), or with immunosuppressive medications such as TNF-alpha inhibitors or systemic or inhaled corticosteroids (used for > 5 consecutive days), within 2 weeks prior to screening. Refer to the SRM for details.
12. Unavoidable treatment with prohibited concomitant medications (see SRM)
13. Participants with the following abnormal laboratory values at screening as graded by the enhanced Common Terminology Criteria for Adverse Events (CTCAE v 5 2017):
  - a. haemoglobin <10.0 g/dL; this criterion may be adjusted following DEC review (see Section 11).
  - b. thrombocytopenia grade 2 or greater (under  $50 \times 10^9$  cells/L);
  - c. serum potassium grade 2 or greater (<3.0 mEq/L);

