### 8.1.3. Haematology Stopping Criteria

IP will be discontinued for a subject if the following haematology stopping criteria are met (confirmed on two samples or at the discretion of the investigator in consultation with the medical monitor) and participants should be followed up until values are not clinically significant.

- A reduction in haemoglobin to below 8.0 g/dL; this criterion may be adjusted following DEC review (see Section 11).
- A reduction in neutrophil count to below 500/mm^3 ( $0.5 \times 10^9/L$ )

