The primary endpoint may be analysed once data is available for 12 evaluable subjects, as per the sample size re-estimation calculations, on the second consecutive cohort that reaches or exceeds the target PK plasma exposure for efficacy (based on the murine infection model), and subsequent cohorts. The purpose of this efficacy analysis is to optimise dosing for subsequent cohorts (e.g. to help estimate the dose response curve) as well as to aid internal decision making.

The DEC is empowered to take the following decisions for subsequent cohorts:

- To select a higher dose (including a loading dose that may be given over 1 or more days) within the limits defined in Section 5.6.
- To select a dose lower than, or the same as, a preceding dose.
- To stop dosing.
- To include additional pharmacokinetic assessments.
- To include additional timepoints for an existing safety assessment.
- To adjust the haemoglobin exclusion and stopping criteria if no haematological abnormalities are observed in the review of safety data from the highest dose cohort (Cohort 3). For the subsequent cohort(s) receiving a lower dose of GSK3036656, the haemoglobin exclusion criterion will be lowered to <8.0 g/dL, and the haemoglobin stopping criterion will be lowered to <6.0 g/dL. Patients with a confirmed haemoglobin <8.0g/dL after randomisation will require enhanced observations, with a repeat haemoglobin level and discussion of patient status with the GSK medical monitor.

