## 12.8. Appendix 8: Values of Potential Clinical Importance

### 12.8.1. Laboratory Values

Haematology				
Laboratory Parameter	Units	Category	Clinical Concern Range	
			Low Flag (< x)	High Flag (>x)
Hematocrit	Ratio of 1	Male		0.54
		Female		0.54
		Change from Baseline	Decrease of 0.075	
Haemoglobin	g/L	Male	75	180
		Female	75	180
		Change from Baseline	Decrease of 25	
Lymphocytes	x10  / L		0.8	
Neutrophil Count	x10  / L		0.5	
Platelet Count	x10  / L		100	550
While Blood Cell Count (WBC)	x10  / L		3	20

Clinical Chemistry				
Laboratory Parameter	Units	Category	Clinical Concern Range	
			Low Flag (< x)	High Flag (>x)
Albumin	g/L		20	
Calcium	mmol/L		2	2.75
Creatinine	%	Change from Baseline		Increase of 30%
Glucose	mmol/L		3	11
Potassium	mmol/L		3	5.5
Sodium	mmol/L		130	150

Liver Function				
Test Analyte	Units	Category	Clinical Concern Range	
ALT / SGPT	IU/L	High	≥ 3x ULN	
AST / SGOT	IU/L	High	≥ 3x ULN	
AlkPhos	IU/L	High	≥ 2x ULN	
T Bilirubin	µmol/L	High	≥ 1.5x ULN	
T. Bilirubin + ALT	µmol/L	High	1.5x ULN T. Bilirubin	

Liver Function			
Test Analyte	Units	Category	Clinical Concern Range
			+
	U/L		≥ 2x ULN ALT

ULN = Upper Limit of Normal; ALT=Alanine Aminotransferase; AST=Aspartate Aminotransferase; SGPT=Serum Glutamic Pyruvic Transaminase; SGOT=Serum Glutamic Oxaloacetic Transaminase; T. Bilirubin=Total Bilirubin

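### The SAP's haemoglobin flags (below 75 g/L, or a fall of 25 g/L) can miss a confirmed value below the protocol's 8.0 g/dL action level

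*SAP*

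**What the plan says.** **Protocol, original criteria.** Section 6.2, criterion 13a, excludes "haemoglobin <10.0 g/dL; this criterion may be adjusted following DEC review". Section 8.1.3 discontinues study drug for "A reduction in haemoglobin to below 8.0 g/dL; this criterion may be adjusted following DEC review". The stop applies when "confirmed on two samples or at the discretion of the investigator in consultation with the medical monitor".

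**Protocol, adjusted criteria.** Section 11 lets the Dose Escalation Committee lower the limits for later, lower-dose cohorts if Cohort 3 shows no haematological abnormalities. Exclusion then moves to <8.0 g/dL and stopping to <6.0 g/dL. The 8.0 g/dL level stays in use for monitoring: "Patients with a confirmed haemoglobin <8.0g/dL after randomisation will require enhanced observations".

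**SAP.** Section 12.8.1 sets the haemoglobin criteria of potential clinical importance (PCI). The low flag is a value <75 g/L, the high flag is >180 g/L, and the change-from-baseline row reads "Decrease of 25", in g/L. Table 3.13 (worst-case haematology) counts participants by these criteria. Listing 23 shows the flagged haematology values, and Listing 22 shows all haematology data for any participant with at least one flagged value.

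**The concern.** Reduction in red cell count is the first risk listed for the compound in protocol 3.3.1. Protocol 10.3.2 commits to reporting worst-case laboratory results as the number and percentage of participants per dose group, and Table 3.13 does this through the PCI flags. The protocol also reads such flags as evidence. On haemoglobin in the first-in-human study it says: "None of the values hit potential clinical importance (PCI) criteria, and declines were not clinically relevant".

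The haemoglobin flag sits below the level at which the protocol acts. A participant can meet the stopping rule, or the enhanced-observation rule in an adjusted cohort, and still be counted in Table 3.13 as having no low haemoglobin of potential clinical importance. With the 9 participants per GSK3036656 arm supported in protocol 10.1.2, one such case changes a dose group's count from 1/9 (11%) to 0/9. That shows how far one case can move a small group's count. It does not say how likely the case is.

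**Working it through.** The documents give no figure of their own to reproduce here. The check compares thresholds.

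**Inputs in common units (1 g/dL = 10 g/L)**
- Protocol action level: 8.0 g/dL = 80 g/L (8.1.3; Section 11).
- Lowest eligible screening value: 10.0 g/dL = 100 g/L (6.2), or 8.0 g/dL = 80 g/L if adjusted (Section 11).
- Adjusted stopping limit: 6.0 g/dL = 60 g/L (Section 11).
- SAP flags: value <75 g/L, or a fall of 25 g/L (12.8.1).

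**Condition for a missed case.** Write B for baseline and N for the confirmed nadir. The trigger is met with no flag when N < 80, N ≥ 75 and B − N < 25 all hold. The first and third together give B < 80 + 25 = 105 g/L.

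**Counting whole-number pairs (B, N).** The SAP does not say whether the change flag means a fall of at least 25 or of more than 25, so both readings were counted.

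| Entry limit | Change flag read as | Unflagged baselines | Unflagged nadirs | Pairs |
|---|---|---|---|---|
| ≥100 g/L | ≥25 | 100–103 | 76–79 | 10 |
| ≥100 g/L | >25 | 100–104 | 75–79 | 15 |
| ≥80 g/L | ≥25 | 80–103 | 75–79 | 110 |
| ≥80 g/L | >25 | 80–104 | 75–79 | 115 |

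**Examples**
- 100 to 78 g/L: below 80, so the trigger is met if confirmed. It is not below 75, and the fall is 100 − 78 = 22. Neither flag fires.
- 102 to 79 g/L: the fall is 23. Neither flag fires.
- 105 to 79 g/L: the fall is 26. The change flag fires.

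**What each regime implies.** Under the original criteria the gap concerns stopping. It needs a baseline of 100 to just under 105 g/L and a fall of more than 20 but less than 25 g/L. Under the adjusted criteria the gap is wider but concerns enhanced observation only. The stop at 60 g/L lies below 75 and is always flagged. One caveat applies to both lower bounds: entry limits are applied at screening, while SAP 5.2 takes the latest pre-dose value as baseline. A participant whose pre-dose value is below the screening value widens the zone.

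**Comparison with the other numeric stopping rules**

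| Parameter | SAP flag (12.8.1, 12.8.2) | Protocol stop (8.1.2, 8.1.3, Appendix 7) |
|---|---|---|
| Neutrophils | <0.5 × 10⁹/L | <0.5 × 10⁹/L |
| QTcF, absolute | >450 msec | >500 msec |
| QTcF, increase | >60 msec | >60 msec |
| ALT | ≥3×ULN | ≥5×ULN, or ≥3×ULN with further conditions |
| Haemoglobin, original criteria | <75 g/L or fall of 25 g/L | <80 g/L |

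Only for haemoglobin can the stopping level be reached without a flag.

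**After the fix.** With a category at <80 g/L, the number of trigger-meeting pairs left unflagged is 0 under both entry limits.

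**The case against.** The best reply is that the consequence is small and the case stays visible. Most of that stands.

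- **Visibility.** A reader might infer that a stop for low haemoglobin would surface only in a discontinuation listing, or that the safety output as a whole could show no trace of it. The documents do not support that. Table 1.3 counts treatment discontinuations with reasons. Table 3.12 summarises haematology changes from baseline, and Figure 3.4 plots a line for each participant. Neither is restricted by PCI flags. Protocol 9.4.5 has clinically significant laboratory changes recorded as adverse events, so Tables 3.1 and 3.5 and Listings 12 and 17 may show the case too. Listing 22 includes the participant if any other haematology parameter is flagged.
- **Confirmation.** A reader might infer that every single value from 75 to 79.9 g/L sets off a protocol action. It does not. Section 8.1.3 asks for two samples or a discretionary decision with the medical monitor, and Section 11 asks for a confirmed value.
- **Frequency.** A reader might infer that entrants cluster near the floor, because the Amendment 5 rationale reports many screen failures just under 10.0 g/dL. That describes people who were not enrolled. The one clinical change reported, a mean of −4.9 g/L in the 15 mg repeat-dose cohort of the first-in-human study, is far from the 20 to 25 g/L fall needed under the original limit.
- **First-in-human reassurance.** The PCI limits used in that study are not in these documents, so its result says nothing about how a 75 g/L flag performs.
- **Purpose.** Nothing requires PCI limits to equal protocol triggers. The affected displays belong to the final deliverable only, and stopping and observation act on the values themselves.

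What remains is narrower: the table and listings meant to pick out important haemoglobin values can omit one that the protocol itself acts on, and the SAP gives no reason for the difference.

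**Conclusion.** The mismatch is real and modest in severity. It affects the PCI classification of haemoglobin in Table 3.13 and Listing 23, and inclusion in Listing 22 when no other haematology parameter is flagged. It does not affect participant safeguards, dose decisions or efficacy results.

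The unflagged zone is a confirmed nadir of 75 to just under 80 g/L with a fall of less than 25 g/L. A stop without a haemoglobin flag under the numeric criterion is confined to the original criteria and a 5 g/L band of baselines. The broader band, from 80 g/L, arises only if the committee adjusts the criteria, and there it means enhanced observation without a flag. Reading the broad band as a stopping problem would merge the two regimes.

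These bounds assume that baseline is not below the entry limit. The finding holds under either reading of the change flag. The documents do not allow an estimate of how many participants fall in the zone. No view is taken on which clinical threshold is right; the point is that SAP 12.8.1 and protocol 8.1.3 and Section 11 should be reconciled for reporting.

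**What to change.** In SAP 12.8.1, add a haemoglobin reporting category at <80 g/L and keep <75 g/L as a deeper category. Every value below the protocol's 8.0 g/dL level then appears in Table 3.13 and Listings 22 and 23. In the same edit, state whether the change flag means a fall of at least 25 or of more than 25 g/L.

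The cost is one added row in an appendix and the matching programming. No new data are needed, and no stopping, entry or observation rule changes. The downside is more flagged values. Unconfirmed single results below 80 g/L would be included, and in cohorts with entry from 80 g/L so would trivial falls such as 81 to 79 g/L. The retained <75 g/L tier and the change-from-baseline flag help a reader separate those from larger declines.

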**12.8.2. ECG**

ECG Parameter	Units	Clinical Concern Range	
		Lower	Upper
Absolute			
Absolute QTcF Interval	msec		>450
Absolute PR Interval	msec	< 110	>220
Absolute QRS Interval	msec	< 75	>110
Change from Baseline			
Increase from Baseline QTcF	msec		>60

QTcF=QT Interval corrected for heart rate (Fridericia); PR=Electrocardiographic PR Interval

**12.8.3. Vital Signs**

Vital Sign Parameter (Absolute)	Units	Clinical Concern Range	
		Lower	Upper
Systolic Blood Pressure	mmHg	< 85	>160
Diastolic Blood Pressure	mmHg	< 45	>100
Heart Rate	bpm	< 40	>110
Respiratory Rate	Breaths/min	10	28
Temperature	Degrees C	35.0	37.9

## 12.9. Appendix 9: Abbreviations & Trade Marks

### 12.9.1. Abbreviations

Abbreviation	Description
%CVb	Between participant geometric coefficient of variation
AE	Adverse Event
AIC	Akaike's Information Criteria
ALT	Alanine Aminotransferase
AST	Aspartate Aminotransferase
AUC(0-t)	Area under the concentration-time curve from time of dosing to last quantified concentration, regardless of time.
AUC(0-24)	Area under the concentration-time curve from time of dosing extrapolated to 24 hours
BMI	Body Mass Index
BP	Blood Pressure
C τ	Trough Concentration
CFU	Colony Forming Units
C max	Maximum observed plasma drug concentration
CS	Compound Symmetry
CSR	Clinical Study Report
CPMS	Clinical Pharmacology Modelling & Simulation
CPSSO	Clinical Pharmacology Science and Study Operations
DAP	Data Analysis Plan
DBF	Database Freeze
DBR	Database Release
DS	Drug sensitive (i.e. Rifampicin-Susceptible)
EBA	Early Bactericidal Activity
ECG	Electrocardiogram
eCRF	Electronic Case Report Form
EudraCT	European Clinical Trials Database
FDA	Food and Drug Administration
FDAAA	Food and Drug Administration Amendments Act
FDG	Fluorodeoxyglucose
FPD	Future Pipelines Discovery
GCSP	Global Clinical Safety and Pharmacovigilance
GSK	GlaxoSmithKline
HPD	Highest Posterior Density
ICH	International Conference on Harmonization
IDSL	Integrated Data Standards Library
MedDRA	Medical Dictionary for Regulatory Activities
Mtb	Mycobacterium tuberculosis
PCI	Potential Clinical Importance
PDMP	Protocol Deviation Management Plan
CCI	
PK	Pharmacokinetic

Abbreviation	Description
QD	Once Daily
QTc	QT Interval Corrected for Heart Rate
QTcF	Frederica's QT Interval Corrected for Heart Rate
RAP	Reporting and Analysis Plan
SAC	Statistical Analysis Complete
SAE	Serious Adverse Event
SERM	Safety Evaluation and Risk Management
SGPT	Serum Glutamic Pyruvic Transaminase
SGOT	Serum Glutamic Oxaloacetic Transaminase
SoC	Standard-of-Care
SOP	Standard Operating Procedure
SRT	Safety Review Team
TB	Tuberculosis
tmax	Time to maximum observed plasma drug concentration
TNTC	Too Numerous To Count
TTP	Time to Sputum Culture Positivity
ULN	Upper Limit of Normal
UN	Unstructured
VC	Variance Components
WBC	White Blood Cell Count

**12.9.2. Trademarks**

Trademarks of the GlaxoSmithKline Group of Companies
NONE

Trademarks not owned by the GlaxoSmithKline Group of Companies
SAS
WinNonlin

## 12.10. Appendix 10: List of Data Displays

### 12.10.1. Data Display Numbering

The following numbering will be applied for RAP generated displays:

Section	Tables	Figures
Study Population	1.1 to 1.18	None
Efficacy	2.1 to 2.10	2.1 to 2.5
Safety	3.1 to 3.23	3.1 to 3.5
Pharmacokinetic	4.1 to 4.5	4.1 to 4.7
Section	Listings	
ICH Listings	1 to 31	
Other Listings	32 to 39	

### 12.10.2. Mock Example Shell Referencing

Non-integrated data standards library (IDSL) specifications will be referenced as indicated and if required example mock-up displays provided in [Appendix 11](#): Example Mock Shells for Data Displays.

Section	Figure	Table	Listing
Study Population	POP_Fn	POP_Tn	POP_Ln
Efficacy	EFF_Fn	EFF_Tn	EFF_Ln
Safety	SAFE_Fn	SAFE_Tn	SAFE_Ln
Pharmacokinetic	PK_Fn	PK_Tn	PK_Ln

**NOTES:**

- Non-Standard displays are indicated in the 'IDSL / Example Shell' column as '[Non-Standard] + Reference.'

### 12.10.3. Deliverables

Delivery	Description
DE	Dose Escalation Efficacy Analysis
SAC	Final Statistical Analysis Complete

Note, all displays (Tables, Figures and Listings) will use the term 'subjects', in place of participants.

## 12.10.4. Study Population Tables

Study Population Tables					
No.	Population	IDSL / Example Shell	Title	Programming Notes	Deliverable
Subject Disposition					
1.1.	Safety	ES1	Summary of Subject Disposition for the Subject Conclusion Record	ICH E3, FDAAA, EudraCT Add footnote: "5mg=15mg loading dose and 5mg maintenance dose, Xmg=..."	DE, SAC
1.2.	Safety	ES1	Summary of Subject Status and Subject Disposition for the Study Conclusion Record by Relationship to COVID-19 Pandemic	Page by COVID-19 relationship Yes/No.	SAC
1.3.	Safety	SD1	Summary of Treatment Status and Reasons for Discontinuation of Study Treatment	ICH E3	SAC
1.4.	Safety	SD1	Summary of Treatment Status and Reasons for Discontinuation of Study Treatment by Relationship to COVID-19 Pandemic		SAC
1.5.	Safety	ES4	Summary of Subject Disposition at Each Study Epoch	ICH E3 Display by cohort (i.e. epoch=cohort).	SAC
1.6.	Screened	ES6	Summary of Screening Status and Reasons for Screen Failure	Journal Requirements	SAC
1.7.	Enrolled	NS1	Summary of Number of Participants by Country and Site ID	EudraCT/Clinical Operations	SAC
Protocol Deviation					
1.8.	Safety	DV1	Summary of Important Protocol Deviations	ICH E3	SAC
1.9.	Safety	DV1	Summary of Important COVID-19 Related Protocol Deviations		SAC
1.10.	Safety	DV1	Summary of Important Non COVID-19 Related Protocol Deviations		SAC
Population Analysed					

Study Population Tables					
No.	Population	IDSL / Example Shell	Title	Programming Notes	Deliverable
1.11.	Screened	SP1	Summary of Study Populations	IDSL Include all columns in the IDSL template.	DE, SAC
1.12.	Safety	SP2A	Summary of Exclusions from the Efficacy Population	IDSL	DE, SAC
1.13.	Safety	SP2A	Summary of Exclusions from the PK Population	IDSL	SAC
Demographic and Baseline Characteristics					
1.14.	Safety	DM1	Summary of Demographic Characteristics	ICH E3, FDAAA, EudraCT Include BMI and smoking status.	SAC
1.15.	Enrolled	DM11	Summary of Age Ranges	EudraCT	SAC
1.16.	Safety	DM5	Summary of Race and Racial Combinations	ICH E3, FDA, FDAAA, EudraCT	SAC
Prior and Concomitant Medications					
1.17.	Safety	MH1	Summary of Past Medical Conditions	ICH E3	SAC
1.18.	Safety	MH1	Summary of Current Medical Conditions	ICH E3	SAC

12.10.5. Efficacy Tables

Efficacy: Tables					
No.	Population	IDSL / Example Shell	Title	Programming Notes	Deliverable
CFU					
2.1.	Efficacy	Non-standard EFF_T1	Summary Table of log 10 CFU Counts Over Time		DE, SAC
2.2.	Efficacy	Non-standard EFF_T1	Summary Table of Change from Baseline in log 10 CFU Counts Over Time	Include baseline row similar to LB1 template.	DE, SAC
2.3.	Efficacy	Non-standard EFF_T2	Rate of Change in log 10 CFU by Treatment – Mixed Model Analysis	For dose escalation analysis, calculate EBA CFU(0-14) only. Supportive SAS output to be produced and archived	DE, SAC
2.4.	Efficacy	Non-standard EFF_T3	Node and Slope Parameter Estimates for log 10 CFU by Treatment – Bi-linear Bayesian Model Analysis	For dose escalation analysis, calculate EBA CFU(0-14) only. Supportive SAS output to be produced and archived	DE, SAC
2.5.	Efficacy	Non-standard EFF_T2	Rate of Change in log 10 CFU by Treatment – Mixed Model Analysis – Withdrawn/Replaced Participants Excluded	For endpoints CFU(0-14) and CFU(2-14) only. Supportive SAS output to be produced and archived	SAC
2.6.	Efficacy	Non-standard EFF_T4	Summary of Covariate and Treatment*Covariate Interaction Significance For log 10 CFU(0-14) Mixed Model Analysis	Supportive SAS output to be produced and archived	SAC
TTP					
2.7.	Efficacy	Non-standard EFF_T1	Summary Table of TTP Counts Over Time		SAC

